1.4. Sample Size and Power

With 26 evaluable subjects (13 in each sequence), the estimated two-sided 90% CI of the GLSM ratio of test versus reference treatments, with regards to AUC_{inf} , AUC_{last} , and C_{max} , will be within [70%, 143%] with $\geq 85\%$ probability, if the true GLSM ratio is 1.0. This is assuming a standard deviation (SD) of differences of no more than 0.569 on a natural logarithm scale, supported by PK data from Study GS-US-402-2102. With 4 subjects for overage, a total sample size of 30 subjects will be required.

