1.1.6. Rosuvastatin

Rosuvastatin (ROS), is a HMG-CoA reductase inhibitor used in patients with elevated cholesterol and with a risk of cardiovascular disease. In this study, ROS 10 mg (1 × 10 mg tablet) will be administered as a single dose to healthy participants to collectively assess OATP1B1/1B3 and breast cancer resistance protein (BCRP) activity in the presence and absence of filgotinib {Chu 2018, Giacomini 2010}.

The relative contribution of OATP and BCRP in determining in vivo ROS disposition is not known. However, emerging data on the significance of SLCO1B1 polymorphisms and associated statin-induced myopathy provides compelling evidence on the importance of OATP in ROS PK {Elsby 2012, Meyer zu Schwabedissen 2009, Neuvonen 2010, Pasanen 2007}. Collectively, use of both PRA and ROS as probes in this study will allow for a better understanding and/or discrimination of the effects of filgotinib on OATP and BCRP.

Rosuvastatin can be taken with or without food, any time of the day, over a dose range of 5 to 40 mg once daily. Rosuvastatin peak plasma concentrations are reached in 3 to 5 hours after oral dosing, and administration with food does not affect the AUC of ROS. Rosuvastatin is not extensively metabolized and the major metabolite, N-desmethyl rosuvastatin, is formed principally by CYP2C9; this metabolite displays one-sixth to one-half of the HMG-CoA-reductase inhibitory activity of the parent. Overall, greater than 90% of active plasma HMG-CoA-reductase inhibitory activity is accounted for by the parent compound. The elimination half-life of ROS is approximately 19 hours. Rosuvastatin clearance is not dependent on metabolism by CYP3A4 to a clinically significant extent.

Further information regarding ROS is available in the package insert.

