8.3.1.3. Pharmacokinetics Analysis Set

The PK Analysis Set will include all randomized participants who received at least 1 dose of study drug and had at least 1 nonmissing PK concentration datum reported by PK laboratory for each respective analyte.

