8.6. Pharmacokinetic Analysis

An analysis of variance (ANOVA) using a mixed-effects model with treatment, period, and sequence as fixed effects and participant as a random effect will be fitted to the natural logarithmic transformation of PK parameters (AUC_{last} , AUC_{inf} , C_{max}) for each analyte. Two-sided 90% CIs will be calculated for the ratios of geometric least-squares means (GLSMs) of primary PK parameters between test (Treatment B) versus reference (Treatment A) treatments.

Lack of PK interaction between the test and reference treatments will be concluded if the 90% CIs for the GLSM ratios are contained within the 0.70 and 1.43 range for ATV, PRA, and ROS AUC and C_{max} . Additional analyses may be performed if useful and appropriate.

Plasma concentrations and PK parameters AUC_{last} , AUC_{inf} , C_{max} , $\%AUC_{exp}$, C_{last} , T_{max} , T_{last} , $t_{1/2}$, CL/Z , λ_z and V_z/F will be listed and summarized for ATV, PRA, and ROS using descriptive statistics by treatment.

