8.7. Sample Size

With 26 evaluable participants, the estimated two-sided 90% CI of the GLSM ratio of test versus reference treatments, with regards to AUC_{inf} , AUC_{last} , and C_{max} , will be within [70%, 143%] with $\geq 85\%$ probability, if the true GLSM ratio is 1.0. This is assuming a standard deviation (SD) of differences of no more than 0.569 on a natural logarithm scale, supported by PK data from Study GS-US-402-2102. With 4 participants for overage, a total sample size of 30 participants will be required.

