3.1.3. Pharmacokinetic Analysis Set

The PK Analysis Set will include all randomized subjects who received at least 1 dose of study drug and had at least 1 non-missing PK concentration datum reported by PK laboratory for each respective analyte. This is the primary analysis set for all PK analyses.

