8.1.2.2. Statistical Methodology

8.1.2.2.1. 8.1.3.2.1 Analysis of Drug-Drug Interaction

An analysis of variance (ANOVA) using a mixed-effects model with treatment, period, and sequence as fixed effects and subject as a random effect will be fitted to the natural logarithmic transformation of PK parameters (AUC_{last} , AUC_{inf} , C_{max}) for ATV versus ATV + FIL, and PRA/ROS versus PRA/ROS+FIL. The same model will be fitted to the natural logarithmic transformation of molar ratio of metabolite to parent exposure (2-OH-ATV to ATV) of PK parameters (AUC_{last} , AUC_{inf} , and C_{max}) for ATV versus ATV + FIL. Additional analyses may be performed if useful and appropriate. Two-sided 90% CIs will be calculated for the ratios of geometric least-squares means (GLSMs) of primary PK parameters between test (Treatment B) versus reference (Treatment A) treatments.

Lack of PK interaction between the test and reference treatments will be concluded if the 90% CIs for the GLSM ratios are contained within the 70% - 143% range for ATV, 2-OH-ATV, PRA, and ROS AUC and C_{max} .

Treatment comparisons of interest are shown in [Table 8-3](#).

Table 8-3. Statistical Comparisons for Pharmacokinetic Analyses

Analyte	Parameter	Comparison (mean [%CV])		(% GLSM ratio and 90% CI)
		Test	Reference	
ATV	AUC _{last} AUC _{inf} C _{max}	ATV+FIL	ATV	Lack of effect boundary: 70% - 143%
2-OH-ATV		PRA/ROS+FIL	PRA/ROS	
PRA				
ROS				
Molar ratio of 2-OH-ATV to ATV	AUC _{last} / AUC _{last} AUC _{inf} / AUC _{inf} C _{max} / C _{max}	ATV+FIL	ATV	

The statistical model will include treatment period and treatment sequence as a fixed effect and subject as a random effect. The following SAS PROC MIXED code will provide the treatment comparison analysis and the 90% CI calculations for natural log-transformed PK parameters.

```
proc mixed;
  where param='AUClast';
  class treat period sequence subjid;
  model lnest = treat period sequence / ddfm=kr;
  random subjid;
  lsmeans treat / diff cl alpha = 0.1;
  estimate 'Test versus Reference' treat -1 1 / cl alpha = 0.10;
  ods output Estimates = LS_Diffs LSMeans = LS_Means CovParms MSE;
run;
```

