8.1.4. Changes From Protocol-Specified PK Analyses

Rather than 26 subjects (13 in each sequence), as specified in the protocol, 25 evaluable subjects (12 in one sequence and 13 in another sequence) was randomized and completed the study. The probability of the estimated two-sided 90% CI of the GLSM ratio of test versus reference treatments, with regards to AUC_{inf} , AUC_{last} , and C_{max} , will be within [70%, 143%] changed from $\geq 85\%$ to $\geq 83\%$.

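### Do the stated 85% and 83% probabilities overstate the chance of meeting a rule that needs both the AUC and Cmax intervals inside 70% to 143%?

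*SAP*

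**What the plan says.** Protocol 8.7 and SAP 1.4 give the same justification. In the SAP it opens "With 26 evaluable subjects (13 in each sequence), the estimated two-sided 90% CI of the GLSM ratio of test versus reference treatments" and says that this interval will lie within 70% to 143% with at least 85% probability at a true ratio of 1.0, with regard to AUCinf, AUClast and Cmax. On variability, Protocol 8.7 says "This is assuming a standard deviation (SD) of differences of no more than 0.569 on a natural logarithm scale", citing Study GS-US-402-2102. SAP 8.1.4 reports that "25 evaluable subjects (12 in one sequence and 13 in another sequence) was randomized and completed the study" and lowers the probability to at least 83%.

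The decision rule stands elsewhere. Protocol 8.6 concludes lack of interaction if the 90% CIs are "contained within the 0.70 and 1.43 range for ATV, PRA, and ROS AUC" and Cmax. SAP 8.1.2.2 has them "contained within the 70% - 143% range for ATV, 2-OH-ATV, PRA, and ROS AUC" and Cmax, which adds the atorvastatin metabolite.

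Neither document says in so many words whether the conclusion is drawn per probe or for the study as a whole. The analysis sets are by analyte: a participant qualifies who "had at least 1 nonmissing PK concentration datum reported by PK laboratory for each respective analyte" (Protocol 8.3.1.3; SAP 3.1.3 has the same condition). Protocol 1.1.6 says that using both pravastatin and rosuvastatin helps with "discrimination of the effects of filgotinib on OATP and BCRP". Concluding one probe at a time is therefore the natural reading.

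**The concern.** The probability is stated for one interval, while the rule refers to several. Two events that each have probability 0.857 do not both occur with probability 0.857 unless they coincide almost perfectly. The sample size text lists three parameters in the same sentence as the 85%, and it does not say that the figure applies to each separately. A reader could take it as the chance of declaring lack of interaction for a probe that is truly unaffected.

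What would be at stake is the false-negative rate. Someone who reads at least 83% as the chance of meeting the rule would expect an unaffected probe to miss it at most 17% of the time. If the true miss rate were nearer 30%, an interval just outside the bounds could be over-read as a sign of interaction.

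**Working it through.** **Inputs.** Bounds 0.70 and 1.43, two-sided 90% CI, true ratio 1.0, SD of differences at the 0.569 ceiling (Protocol 8.6 and 8.7, SAP 1.4). Subjects: 13 + 13 (SAP 1.4) and 12 + 13 (SAP 8.1.4). Model: two-period crossover on the log scale with treatment, period and sequence (SAP 8.1.2.2), so df = n − 2. The AUC-Cmax correlation and the SDs by parameter are not in the documents, so they are varied as assumptions.

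**Step 1: reproduce the stated figures for one interval.**

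- SE = (SD/2) × √(1/n1 + 1/n2)
- 13 + 13: 0.2845 × √(1/13 + 1/13) = 0.1116; t(0.95, 24) = 1.711; expected half-width 1.711 × 0.1116 = 0.191
- 12 + 13: 0.2845 × √(1/12 + 1/13) = 0.1139; t(0.95, 23) = 1.714; expected half-width 0.195
- Log bounds: ln 0.70 = −0.3567, ln 1.43 = 0.3577

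The interval lies inside when the estimate is above −0.3567 plus the half-width and below 0.3577 minus the half-width. Integrating that probability over the chi-square distribution of the estimated variance gives 0.857 for 13 + 13 and 0.838 for 12 + 13. These match at least 85% and at least 83%. Reading 0.569 as a within-subject SD would give 0.42 for n = 26, so it is the SD of differences, as stated. The published figures are correct single-interval probabilities.

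**Step 2: both intervals inside, both SDs at 0.569.** Simulation of correlated log differences, 200,000 trials per setting, one AUC plus Cmax:

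| AUC-Cmax correlation (assumed) | n = 26 | n = 25 |
|---|---|---|
| 0.3 | 0.74 | 0.71 |
| 0.5 | 0.75 | 0.72 |
| 0.7 | 0.77 | 0.75 |
| 0.9 | 0.81 | 0.78 |
| 0.95 | 0.82 | 0.80 |
| 0.99 | 0.84 | 0.82 |

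If AUClast, AUCinf and Cmax must all pass, with an assumed AUClast-AUCinf correlation of 0.99 and AUC-Cmax correlations of 0.3 to 0.9, the ranges are 0.73 to 0.80 (n = 26) and 0.69 to 0.77 (n = 25).

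**Step 3: SDs below the ceiling.** For two intervals the joint probability is at least p1 + p2 − 1, whatever the correlation. At SD 0.40 one interval has probability 0.9945 (n = 26) or 0.9926 (n = 25). With one SD at 0.569 and the other at 0.40:

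- n = 26: 0.8567 + 0.9945 − 1 = 0.851
- n = 25: 0.8376 + 0.9926 − 1 = 0.830

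So the stated figures hold at any correlation. They also hold at any correlation for a common SD of about 0.516 (n = 26), where each interval has 0.925 and 2 × 0.925 − 1 = 0.85. That SD is about 9% below the ceiling (0.516/0.569 = 0.91). In between, the answer depends on the correlation. With Cmax at 0.569, both AUC SDs at 0.50, all three intervals required and correlations of 0.3 to 0.9, the joint probability is 0.805 to 0.845 (n = 26) and 0.780 to 0.826 (n = 25).

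**The case for a change.** The strongest case for a change starts from the plan's own wording. An SD of no more than 0.569 paired with a probability of at least 85% reads as a guarantee over the whole permitted range. At the top of that range, the guarantee fails for a two-interval rule unless the AUC-Cmax correlation exceeds 0.99. At n = 25 with all three intervals required, an unaffected probe would miss 23% to 31% of the time. The per-probe reading is also the lenient one, since requiring the metabolite or all probes together could only lower the probability. The sponsor thought a fall from 85% to 83% worth declaring, and the possible gap here is larger. Finally, AUC in the rule could mean either or both of two primary parameters.

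The conditional arithmetic stands, and so does the remark that the text would be clearer with the words for each CI, the unit of conclusion and the AUC that counts. What does not stand is the step from there to a defect. The sentence in Protocol 8.7 and SAP 1.4 is about one interval for one ratio, applied to each listed parameter, and for that it is right. The 23% to 31% needs three SDs at exactly the ceiling and correlations no higher than 0.9. A ceiling that covers several parameters need not be reached by all of them. The SDs that would settle it come from a study not available here.

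**Conclusion.** No change follows. The 85% and 83% are correct for what they describe, a single 90% CI at an SD of differences of 0.569 and a true ratio of 1.0. A lower joint probability for a probe is a possibility, not a demonstrated shortfall. It is about 0.74 to 0.82 (n = 26) and 0.71 to 0.80 (n = 25) if both SDs sit at the ceiling and the AUC-Cmax correlation is 0.3 to 0.95. There is no shortfall for one AUC plus Cmax if either SD is near 0.40.

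Nor would anything be gained. SAP 8.1.4 says that the 25 subjects have completed, so the sample size cannot move. Requiring every interval to pass does not inflate type I error. All ratios and intervals are reported by analyte and parameter, and a probe outside the bounds will be interpreted from its own estimate and interval, not from planning power. Stating the unit of conclusion is detail that analysts can supply sensibly from the by-analyte structure. A supplementary joint probability would rest on correlations that the documents do not give. Adding for each CI to the sample size text is an optional clarification that alters no analysis, result or conclusion.

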2. TYPE OF PLANNED ANALYSIS

2.1. Data Monitoring Committee Analyses

This study does not have a data monitoring committee (DMC). Therefore, no analyses will be conducted for the DMC.

2.2. Interim Analysis

No interim analysis is planned.

2.3. Final Analysis

After all subjects have completed the study, outstanding data queries have been resolved or adjudicated as unresolvable, and the data have been cleaned and finalized, the final analysis of the data will be performed.

2.4. Changes from Protocol-Specified Analysis

No changes from protocol-specified analyses are planned.

3. GENERAL CONSIDERATIONS FOR DATA ANALYSES

Analysis results will be presented using descriptive statistics. For categorical variables, the number and percentage of subjects in each category will be presented; for continuous variables, the number of subjects (n), mean, standard deviation (SD) or standard error (SE), median, first quartile (Q1), third quartile (Q3), minimum, and maximum will be presented.

By-subject listings will be presented for all subjects in the All Randomized Analysis Set and sorted by subject identification (ID) number in ascending order, visit date, and time (if applicable), unless otherwise specified. Data collected on log forms, such as AEs, will be presented in chronological order within subject. The treatment group and treatment sequence to which subjects were initially assigned will be used in the listings.

3.1. Analysis Sets

Analysis sets define the subjects to be included in an analysis. Analysis sets and their definitions are provided in this section. The analysis set will be identified and included as a subtitle of each table, figure, and listing.

For each analysis set, the number and percentage of subjects eligible for inclusion will be provided in the disposition table as detailed in Section 4. A listing of reasons for exclusion from analysis sets will be provided by subject.

3.1.1. All Randomized Analysis Set

The All Randomized Analysis Set includes all subjects randomized into the study after screening. This is the primary analysis set for safety listings.

3.1.2. Safety Analysis Set

The Safety Analysis Set will include all randomized subjects who received at least 1 dose of study drug. Subjects who received treatment other than that to which they were assigned will be analyzed according to the treatment received. This is the primary analysis set for safety analyses.

3.1.3. Pharmacokinetic Analysis Set

The PK Analysis Set will include all randomized subjects who received at least 1 dose of study drug and had at least 1 non-missing PK concentration datum reported by PK laboratory for each respective analyte. This is the primary analysis set for all PK analyses.

3.2. Missing Data and Outliers

3.2.1. Missing Data

In general, missing data will not be imputed unless methods for handling missing data are specified.

The handling of missing or incomplete dates for AE onset is described in Section 7.1.6.2.

3.2.2. Outliers

Outliers of non-PK data will be identified during the data management and data analysis process, but no sensitivity analyses will be conducted. All data will be included in the data analysis.

3.3. Data Handling Conventions and Transformations

In general, age (in years) on the date of the first dose of study drug will be used for analyses and presentation in listings. If an enrolled subject was not dosed with any study drug, the enrollment date will be used instead of the first dosing date of study drug. If only the birth year is collected on the CRF, “01 July” will be used for the unknown birth day and month for the purpose of age calculation. If only birth year and month are collected, “01” will be used for the unknown birthday.

Non-PK Data that are continuous in nature but are less than the lower limit of quantitation (LLOQ) or above the upper limit of quantitation (ULOQ) will be imputed as follows:

- A value that is 1 unit less than the LLOQ will be used to calculate descriptive statistics if the datum is reported in the form of “< x” (where x is considered the LLOQ). For example, if the values are reported as < 50 and < 5.0, values of 49 and 4.9, respectively, will be used to calculate summary statistics. An exception to this rule is any value reported as < 1 or <0.1, etc. For values reported as < 1 or < 0.1, a value of 0.9 or 0.09, respectively, will be used to calculate summary statistics.
- A value that is 1 unit above the LLOQ will be used to calculate descriptive statistics if the datum is reported in the form of “> x” (where x is considered the LLOQ). Values with decimal points will follow the same logic as the bullet point above.
- The LLOQ will be used to calculate descriptive statistics if the datum is reported in the form of “≤ x” or “≥ x” (where x is considered the LLOQ).

If methods based on the assumption that the data are normally distributed are not adequate, analyses may be performed on transformed data or nonparametric analysis methods may be used, as appropriate.

Natural logarithmic transformation will be used for plasma concentrations and analysis of PK parameters. Plasma concentration values that are below the limit of quantitation (BLQ) will be presented as “BLQ” in the concentration data listing. Values that are BLQ will be treated as 0 at predose time points, and one-half the value of the lower limit of quantitation (LLOQ) at postdose time points for determination of summary and order statistics.

The following conventions will be used for the presentation of summary and order statistics:

- If at least 1 subject has a concentration value of BLQ for the time point, the minimum value will be displayed as “BLQ.”
- If more than 25% of the subjects have a concentration data value of BLQ for given time point, the minimum and Q1 values will be displayed as “BLQ.”

If more than 50% of the subjects have a concentration data value of BLQ for a given time point, the minimum, Q1, and median values will be displayed as “BLQ.”

- If more than 75% of the subjects have a concentration data value of BLQ for a given time point, the minimum, Q1, median, and Q3 values will be displayed as “BLQ.”
- If all subjects have concentration data values of BLQ for a given time point, all order statistics (minimum, Q1, median, Q3, and maximum) and summary statistics will be displayed as “BLQ.”

PK parameters that are BLQ will be imputed as one-half the value of lower limit of quantitation (LLOQ) before log transformation or statistical model fitting.

3.4. Visit Windows

3.4.1. Definition of Predose, Postdose, Study day, and Treatment Day

Predose value is defined as the last available off-treatment value collected prior to the first dose of study drug.

Postdose value is defined as any value collected after the first dose of study drug and before the date of the last dose of study drug plus 30 days.

Study Day is the day relative to the date of the first dose of study drug administration.

Study Day will be calculated from the first dosing date of study drug and derived as follows:

- For postdose study days: assessment date – first dosing date + 1
- For days prior to the first dose: assessment date – first dosing date

Therefore, Study Day 1 is the day of first dose of study drug administration.

Treatment Day is the day relative to the first dose of study drug administration in each period. Treatment Day 1 will be defined as the first dosing date of study drug in each period. Treatment Day will only be used in PK-related listings.

Treatment Day will be calculated from the date of first dose of study drug administration in each period and derived as follows:

- For postdose treatment days: assessment date – first dosing date in each period + 1

- For days prior to the first dose: assessment date – first dosing date in each period.

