7.1.6. Treatment-Emergent Adverse Events

7.1.6.1. Definition of Treatment Emergent

Treatment-emergent adverse events (TEAEs) are defined as any AEs with an onset date on or after the study drug start date and no later than 30 days after permanent discontinuation of study drug. If the AE onset date is the same as the date of study drug start date, the AE onset time must be on or after the study drug start time. If the AE onset time is missing when the start dates are the same, the AE will be considered treatment emergent.

TEAEs with an onset date on/after previous treatment administration date and prior to the next treatment administration date will be attributed to the previous treatment.

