7.2.2.1. Treatment-Emergent Laboratory Abnormalities

Treatment-emergent laboratory abnormalities are defined as values that increase at least 1 toxicity grade from predose at any postdose time point, up to and including the date of last dose of study drug plus 30 days for subjects who permanently discontinued study drug. If the relevant predose laboratory value is missing, any abnormality of at least Grade 1 observed within the time frame specified above will be considered treatment emergent.

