7.2.2.2. Summaries of Treatment-emergent Laboratory Abnormalities

The following summaries (number and percentage of subjects) for treatment-emergent laboratory abnormalities will be provided by lab test and by treatment sequence with treatments under the treatment sequence; subjects will be categorized according to the most severe postdose abnormality grade for a given lab test within a treatment:

- Treatment-emergent graded laboratory abnormalities
- Treatment-emergent grade 3 or higher laboratory abnormalities

There will be two ways to summarize treatment-emergent laboratory abnormalities:

- 3) Two treatment sequences will be combined. And the same treatment (FIL, ATV, etc.) from different treatment sequence will be pooled together.
- 4) Two treatment sequences will be summarized separately.

For all summaries of laboratory abnormalities, the denominator is the number of subjects with nonmissing postdose values up to 30 days after last dosing date.

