7.2.3. Liver-Related Laboratory Evaluations

Liver-related abnormalities after initial study drug dosing will be examined and summarized using the number and percentage of subjects who were reported to have the following laboratory test values for postdose measurements:

- Aspartate aminotransferase (AST): (a) > 3 times of the upper limit of reference range (ULN); (b) $> 5 \times$ ULN; (c) $> 10 \times$ ULN; (d) $> 20 \times$ ULN
- Alanine aminotransferase (ALT): (a) $> 3 \times$ ULN; (b) $> 5 \times$ ULN; (c) $> 10 \times$ ULN; (d) $> 20 \times$ ULN
- AST or ALT: (a) $> 3 \times$ ULN; (b) $> 5 \times$ ULN; (c) $> 10 \times$ ULN; (d) $> 20 \times$ ULN
- Total bilirubin: $> 2 \times$ ULN
- Alkaline phosphatase (ALP) $> 1.5 \times$ ULN
- AST or ALT $> 3 \times$ ULN and total bilirubin: (a) $> 1.5 \times$ ULN; (b) $> 2 \times$ ULN

The summary will be provided by treatment sequence with treatments listed thereunder.

There will be two ways to summarize liver-related laboratory abnormalities:

- 5) Two treatment sequences will be combined. And the same treatment (FIL, ATV, etc.) from different treatment sequence will be pooled together.
- 6) Two treatment sequences will be summarized separately.

The summary will include data from all postdose visits up to 30 days after the last dose of study drug. For individual laboratory tests, subjects will be counted once based on the most severe postdose values. For both the composite endpoint of AST or ALT and total bilirubin, subjects will be counted once when the criteria are met at the same postdose visit date. The denominator is the number of subjects in the Safety Analysis Set who have nonmissing postdose values of all relevant tests at the same postdose visit date. A listing of subjects who met at least 1 of the above criteria will be provided.

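### Treatment-emergent laboratory abnormalities have no onset rule, so one that persists unchanged from period 1 into period 2 is counted as emergent under both Treatment A and Treatment B

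*SAP*

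**What the plan says.** SAP 3.4.1 sets the reference value: "Predose value is defined as the last available off-treatment value collected prior to the first dose of study drug". This is one value per participant for the whole study. The same section also defines a day count that restarts in each period, but limits its use: "Treatment Day will only be used in PK-related listings".

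SAP 7.2.2.1 defines treatment-emergent laboratory abnormalities as "values that increase at least 1 toxicity grade from predose at any postdose time point", within a window that closes 30 days after the last dose. SAP 7.2.2.2 gives the counting rule: "subjects will be categorized according to the most severe postdose abnormality grade for a given lab test within a treatment". The tables are made once by sequence, with treatments beneath, and once with the sequences combined, where "the same treatment (FIL, ATV, etc.) from different treatment sequence will be pooled together". For all of them, "the denominator is the number of subjects with nonmissing postdose values up to 30 days after last dosing date". Nothing in these sections says which treatment a draw belongs to, or separates a persisting abnormality from a new one.

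Adverse events have both rules. Under SAP 7.1.6.1, an event starting after one treatment and "prior to the next treatment administration date will be attributed to the previous treatment". SAP 7.1.7 counts an event that runs on into a later period only where it started. Both rules are worded for adverse events alone.

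Laboratory abnormalities are a named secondary endpoint (Protocol 8.1.3, SAP 1.2), and Protocol 8.5.3 promises their incidence by treatment.

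**The concern.** In a crossover, a column headed with a treatment and labelled treatment-emergent will be read as showing what arose on that treatment. Under these rules it shows what was present on that treatment and absent before the study.

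In Sequence BA, an abnormality that arose on filgotinib and lasted would appear as emergent on statin alone. In Sequence AB, one that arose after a statin alone would appear as emergent on filgotinib. Adverse-event and laboratory tables in the same report would carry the same treatment labels but follow opposite conventions, with nothing to tell the reader.

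**Working it through.** The plan gives no figure to reproduce here, so the check applies its rules to its own schedule.

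**Inputs.** Laboratory draw days (Protocol Tables 6-1 and 6-2): AB Days 1, 3, 6, 7, 12, 13, 14, 15, 17; BA Days 1, 5, 6, 7, 8, 9, 11, 18, 20, 23. Dosing days: SAP Table 1-1. Participants: 25, split 12 and 13 (SAP 8.1.4).

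**One hypothetical participant.** In Sequence BA, a test is Grade 0 before Day 1, Grade 1 on Day 11, and still Grade 1 on Day 18 after the atorvastatin dose. Rise from the reference: 1 − 0 = 1 grade on both days. The definition is met on both, so the worst emergent grade is 1 under filgotinib (B) and 1 under atorvastatin alone (A). In Sequence AB, Grade 1 on Day 6 and again on Day 7 after dosing gives the mirror image.

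**Size of one repeat**, assuming all 25 have postdose values:
- pooled column: 1/25 = 4.0 points;
- by-sequence column: 1/13 = 7.7 points or 1/12 = 8.3 points.

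**How far one abnormality can spread.** The SAP gives no assignment rule, so I assigned each draw to the most recent dose. I took all draws as predose, then all as postdose, because the documents do not fix the timing. A predose Day 1 draw precedes all dosing, so it cannot be an onset draw. The five columns are FIL, FIL+ATV, FIL+PRA+ROS, ATV and PRA+ROS, inferred from the SAP's open-ended list. The abnormality is taken to last to the final draw.

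| Sequence, timing | Possible onset draws | In more than one of five columns | In both A and B | Shortest gap between draws that crosses periods |
|---|---|---|---|---|
| AB, predose | 8 | 7 | 3 | 5 days (Day 7 to 12) |
| AB, postdose | 9 | 7 | 3 | 1 day (Day 6 to 7) |
| BA, predose | 9 | 8 | 7 | 2 days (Day 18 to 20) |
| BA, postdose | 10 | 8 | 7 | 7 days (Day 11 to 18) |
| Total | 36 | 30 | 20 | |

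The 2-day figure arises only because a predose Day 18 draw is assigned to filgotinib, last given on Day 11. If the columns are simply A and B, only the 20 cases repeat.

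**Direction of the effect (assumed rates).** Let pA and pB be the proportions with an abnormality arising under A and B, independently, and q the chance that a period 1 abnormality persists into period 2, with half the participants in each sequence.
- Tabulated under A: pA + 0.5·q·pB·(1 − pA).
- Tabulated under B: pB + 0.5·q·pA·(1 − pB).
- Difference, B minus A: (pB − pA)·(1 − q/2).

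With pA = 5% and pB = 20%, the true difference is 15 points. The table would show 13.1 points at q = 25%, 11.3 at q = 50% and 7.5 at q = 100%. None of these rates comes from the documents.

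**The case against.** The case for leaving the plan alone has real content.

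- **Worst grade within a treatment is a recognised, inclusive convention.** A bare onset-only rule could hide an abnormality that began after a statin and was sustained, without worsening, on filgotinib. This stands, and the fix has to provide for it.
- **The cases can be traced.** The by-sequence tables keep treatment order visible, SAP 7.2.1 summarises values by visit, and the SAP 7.2 listings are chronological. Abnormalities that need intervention or change dosing are also recorded as adverse events (Protocol 7.6) and follow the onset rule. This limits the harm but does not correct the tabulated incidence.
- **No formal safety contrast is planned.** The secondary objective concerns filgotinib alone or with the probes, and SAP 7.2 rules out inferential statistics. This stands, so the consequence is descriptive.

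Three stronger readings are tempting, and the documents do not support them.

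1. A reader might infer that the single pre-study reference is the error. It is a defensible reference for emergence and can stay; what is missing is an onset and assignment rule beside it.
2. A reader might infer that the liver table in SAP 7.2.3 repeats cases in the same way, since it has the same layout: "The summary will be provided by treatment sequence with treatments listed thereunder". But that section also says each participant counts a single time per individual test, at the most severe postdose value. It does not say whether that is per participant or per treatment column, so repetition is not established. The table also reports thresholds crossed, not emergence.
3. A reader might take 30 of 36 or 20 of 36 as rates. They are schedule counts that assume persistence to the last draw and weight every onset day and draw timing equally.

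**Conclusion.** The point holds for SAP 7.2.2.1 and 7.2.2.2. Followed as written, they count an abnormality that persists unchanged from period 1 into period 2 as emergent under both A and B, and possibly under several columns if the columns are drug combinations. The repeat across A and B needs only that draws in each period be tabulated under that period's treatment; the number of columns depends on the assignment rule and column structure assumed above.

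The total effect cannot be sized, because the documents give no persistence rate. What can be said is the effect of each repeat, which is not trivial in columns of 12, 13 or 25 people. The consequence stops at descriptive tables of a secondary endpoint; no pharmacokinetic conclusion changes. It is worth correcting because a stated rule misattributes a named endpoint and the remedy is cheap.

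**What to change.** In SAP 7.2.2.1 and 7.2.2.2:

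1. Assign each laboratory value to the most recent treatment dosed before the draw time, with a stated default when the time is missing.
2. Keep the pre-study value as the reference, but count an abnormality as emergent only under the treatment where the grade first rose, and again only if the grade worsens under a later treatment. Judge worsening against the last value before that treatment began. If filgotinib alone is its own column, apply this at the start of each of its three blocks per sequence.
3. Show abnormalities carried over unchanged on a separate line, or with a flag, in the later treatment's column, so that nothing sustained under filgotinib is hidden.
4. Footnote that onset may precede first detection where no draws are scheduled, chiefly AB Days 8 to 11 and BA Days 12 to 17. For example, an abnormality first seen in a postdose draw on AB Day 12 may have begun on filgotinib alone.

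In SAP 7.2.3, state whether the single count is per participant or per treatment column, and flag carried-over elevations.

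The cost is some programming and a slightly more complex table, using samples already scheduled. If the SAP is already final, its Section 1 provides for documenting the change in the study report.
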